8.5.2 Pharmacokinetic Analysis Populations

Per-Protocol (PP): The set of data generated by the subset of subjects who comply with the protocol sufficiently to ensure that these data will be likely to exhibit the effects of treatment, according to the underlying scientific model. Compliance covers such considerations as exposure to treatment, availability of measurements and absence of major protocol violations. Major protocol violators will be identified to the extent possible prior to unblinding by individuals responsible for data collection/compliance, and its analysis and interpretation. Any subjects or data values excluded from analysis will be identified, along with their reason for exclusion, in the CSR. At the end of the study, all subjects who are compliant with the study procedure as aforementioned and have available data from at least one treatment will be included. This population will be used for the PK and target engagement analyses.

8.5.3 Efficacy Analysis Populations

The full analysis set populations FAS are defined as all subjects with a baseline scan with measurable disease by investigator assessment who were administered MK-1966 and SD-101 (FAS). These populations will be used for exploratory analyses of efficacy.

Analysis of response duration is based on all confirmed responders.

8.6 Statistical Methods

8.6.1 Statistical Methods for Efficacy Analyses

The statistical methods for efficacy analyses are documented in a supplemental SAP (sSAP).

8.6.2 Statistical Methods for Safety Analyses

Safety and tolerability will be assessed by clinical review of all relevant parameters including AEs, SAEs, laboratory tests, vital signs, ECG measurements and physical examinations.

DLTs will be listed. DLTs and adverse experiences will be summarized as counts and frequencies for MK-1966 in combination with SD-101 dose level that had at least three subjects treated and listed for other dose levels. The estimate of the DLT rate among subjects treated with the RPTD and the 80% Bayesian probability interval with non-informative prior for the estimate will be provided. Laboratory assessments, vital signs, and other safety endpoints will be summarized as appropriate.

In addition, the broad clinical and laboratory AE categories consisting of the percentage of subjects with any AE, a drug related AE, a serious AE, an AE which is both drug-related and serious, and who discontinued due to an AE will be summarized for dose levels with at least 3 subjects treated and listed for other doses. Percentages of subjects in these categories among subjects treated with RPTD and 80% confidence intervals for the estimated percentages calculated using the Clopper-Pearson method will be provided.

8.6.3 Summaries of Baseline Characteristics, Demographics, and Other Analyses

8.6.3.1 Demographic and Baseline Characteristics

The number and percentage of subjects screened, allocated, the primary reasons for screening failure, and the primary reason for discontinuation will be displayed. Demographic variables, baseline characteristics, primary and secondary diagnoses, and prior and concomitant therapies will be summarized either by descriptive statistics or categorical tables for APaT population, the set of subjects treated with the RPTD dose for combination of MK-1966 with SD-101.

8.6.3.2 Pharmacokinetics and Pharmacodynamics Modeling Analysis

Serum concentrations of MK-1966 will be summarized by planned visit and time for each dose separately; PK parameters will be summarized by dose. Descriptive statistics will be provided for each dose with at least 3 subjects; for other doses, the results will be listed.

Target engagement will be summarized by planned visit and time for each dose separately. Change from baseline in INF-alpha inducible gene expression will be estimated.

The data from the study will be used to quantitatively explore the relationships among pharmacokinetics, target engagement, exploratory biomarkers and tumor response measurements. A modeling analysis plan will be developed separately.

8.6.3.3 Interim Analyses

No interim analyses are planned for this study.

8.6.3.4 Multiplicity

There will be no multiplicity control in this study.

8.6.3.5 Sample Size and Power Calculations

Dose Escalation and Dose Confirmation/Expansion

The primary purpose of the dose escalation and dose confirmation/expansion parts of the trial is to investigate the safety and tolerability of MK-1966 co-administered with SD-101 in adult subjects with advanced malignancies (Parts A-C) and to establish RPTD for MK-1966 co-administered with SD-101.

The final number of subjects enrolled in the dose escalation and confirmation/expansion parts of the study will depend on the empirical safety (DLT) observations, in particular, at what dose is identified as the RPTD. Sample sizes for a few possible scenarios as well as the

estimated time required to enroll all subjects and the time required to determine the MTD are provided below. The time required to estimate the MTD is the time from the first subject's first dose to the end of the 3-week observation period following the first dose of the last subject enrolled in the dose confirmation/expansion part. The study duration is derived as the time from the first subject's first dose to the end of 6-month treatment period following the enrollment of the last subject.

The enrollment time was conservatively estimated assuming that during 3+3 parts and the dose confirmation/expansion a subject can be enrolled every week. The sample size for each malignancy is 20 subjects, for the purpose of efficacy assessment in exploratory objectives.

Scenario 1. No DLTs during Parts A-C. For MK-1966 with SD-101, in a scenario where no DLTs are encountered during the dose escalation and confirmation/expansion parts so that Part A continues to the highest dose in [Table 5](#), the sample size to determine the MTD is 32 subjects (12 in Part A, 20 from Parts B and C). The total sample size is 52 subjects (12 subjects across 3 doses in Part A, 20 subjects on RPTD in Part B, and another 20 subjects on RPTD in Part C).

It will take 52 weeks to enroll 52 subjects in Parts A-C. Thus, in this scenario the enrollment time across Parts A-C is 52 weeks and the time required to determine the MTD is 35 weeks for 32 subjects. The study duration then is approximately 52 weeks + 24 weeks or 1.8 years. If dose escalation stops at a dose below the highest dose, the study might require less than 52 subjects and the enrollment duration shorter than 52 weeks.

Scenario 2: Flat DLT dose response. Suppose dose escalation in Parts A continues to the highest dose with flat dose response so that all 4 doses (including the top one) are given to 6 subjects each in Part A. Also suppose that the top dose is confirmed as the RPTD dose without de-escalation in Parts B and C. Thus, the sample size to determine the MTD is 44 subjects (24 in Part A, 20 in Parts B and C). The total sample size is 64 subjects (24 in Part A, 20 in Part B, and 20 in Part C).

It will take 64 weeks to enroll 64 subjects in Parts A-C. Thus, in this scenario the enrollment time across Parts A-C is 64 weeks and the time required to determine the two MTDs is 47 weeks for 44 subjects. The study duration then is approximately 64 weeks + 24 weeks or 1.8 years.

Any dose de-escalations and/or re-escalations in Parts B and/or C will increase the sample size in this example.

8.6.4 Precision of the DLT rate at RPTD

Since the TPI approach will be used during the dose confirmation/expansion parts B and C, the estimated DLT rate, and its 80% Bayesian Probability Interval (PI) will be calculated from the posterior distribution of the DLT rate at RPTD using the model specified in the TPI approach. If 20 subjects are finally dosed at RPTD during the dose confirmation/expansion stage, the estimated DLT rate and its 80% PI should be similar to one of the rows in [Table 12](#).

Table 12 Precision of the Estimated DLT rates at RPTD

Number of Subjects dosed at RPTD	Number of DLT Events	Estimated DLT Rate	Lower Bound of 80% PI	Upper Bound of 80% PI
20	2	0.10	0.036	0.206
20	3	0.15	0.069	0.267
20	4	0.20	0.105	0.325
20	5	0.25	0.144	0.381
20	6	0.30	0.185	0.435
20	7	0.35	0.228	0.487

Assume non-informative prior distribution of DLT.

8.7 Subgroup Analyses and Effect of Baseline Factors

No subgroup analyses will be performed.

8.8 Compliance (Medication Adherence)

Drug accountability data for trial treatment will be collected during the study. Percent compliance with drug administration will be calculated for each subject for MK-1966 and SD-101 separately.

For MK-1966 and SD-101, percent compliance will be calculated as following:

$$\text{Percent Compliance} = \frac{\text{Number of Doses Taken}}{\text{Number of Doses that Should have been Taken}} \times 100.$$

For MK-1966, “Number of Doses that Should have been Taken” will be calculated as the minimum of the two numbers: 4 and (1 plus the number (integer) of 3-week intervals that fit between the date of the first dose and the date of the last dose of MK-1966).

For SD-101, “Number of Doses that Should have been Taken” will be calculated as 1 plus the number (integer) of 3-week intervals that fit between the date of the first dose and the date of the last dose of SD-101.

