5.2 Trial Treatment(s)

The treatment(s) to be used in this trial are outlined below in [Table 5](#).

Table 5 Trial Treatment for MK-1966 and SD-101

Treatment During Part A: Dose Finding					
Drug	Dose/Potency	Dose Frequency	Route of Administration	Regimen/Treatment Period ^{††}	Use
MK-1966	70 mg 210 mg 700 mg	Day 1, then Q3W	Intravenous over 30 -120 min	Day 1 then Q3W for 7 additional doses	Experimental
SD-101	1 mg 4 mg [†]	Days 1, 8, 15, 22 then Q3W	Intratumorally	Days 1, 8, 15, 22 then Q3W for 6 additional doses	Experimental
Treatment During Part B and C: Expansion Cohort					
Drug	Dose/Potency	Dose Frequency	Route of Administration	Regimen/Treatment Period ^{††}	Use
MK-1966	MTD/MAD	Every 3 weeks	Intravenous over 30 -120 min	Day 1 then Q3W for 7 additional doses	Experimental
SD-101	4 mg [†]	Days 1, 8, 15, 22 then Q3W	Intratumorally	Days 1, 8, 15, 22 then Q3W for 6 additional doses	Experimental

[†] Note, if the 4 mg SD-101 and 70 mg MK-1966 combination (cohort 2) is not tolerated, then the dose of SD-101 for subsequent cohorts (3 & 4) in part A and expansion cohorts (Parts B and C) will be 1 mg.

^{††}When MK-1966 and SD-101 are scheduled at the same time:

1. SD-101 will be administered first.
2. MK-1966 will be administered at least 30 minutes after the SD-101 injection.

Trial treatment should begin on the day of treatment allocation/randomization or as close as possible to the date on which the subject is allocated/assigned.

The investigator shall take responsibility for and shall take all steps to maintain appropriate records and ensure appropriate supply, storage, handling, distribution and usage of trial treatments in accordance with the protocol and any applicable laws and regulations.

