5.2.5 Timing of Dose Administration

Minimal dosing interval between SD-101 dosing must be 5 days. Trial treatment may be administered up to 3 days before or 5 days after the scheduled Day 1 of each cycle, beginning in Cycle 3. Cycle 2 Day 1 may be administered up to 1 day after the scheduled day 1. In addition, dosing interruptions are permitted in the case of medical / surgical events or logistical reasons not related to study therapy (e.g., elective surgery, unrelated medical events, patient vacation, and/or holidays). Subjects should be placed back on study therapy

within 2 weeks of the scheduled interruption, unless otherwise discussed with the Sponsor. The reason for interruption should be documented in the patient's study record.

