Trial Period:	Screening Phase	Cycles 1					Cycle 2			Cycle 3			Cycle 4 (Day 1)	Cycle 5-8 (Day 1)	End of Treatment Period	Post-Treatment	Survival FU	
Treatment Days:	Screening (Visit 1)															Safety Follow-up		
		1	2	3	8	9	15	22	29	36	43	50	57	64		At end of Cycle 8 ^s or time of treatment discon	30 days post end of Treatment Period	Every 12 weeks
Scheduling Window (Days):	-28 to -1							± 3	± 3	± 3	± 3	± 3	± 3	± 3	± 3	± 3	± 3	± 7
Efficacy Measurements																		
irRESIST - melanoma, squamous cell cancer of head and neck, breast cancer with dermal metastasis ^e	X														X ^e	X		
Cheson Criteria – B Cell Lymphoma ^{e, i}	X														X ^e	X		
Tumor Tissue Collection																		
Archival and/or Newly Obtained Tissue Collection ^{d,o}	X							X ^t								X ^t		
Survival Status Telephone Contact																	X ^m	

- a. Height will be measured at Visit 1 only.
- b. For women of reproductive potential, a urine pregnancy test will be performed within 72 hours of receiving the first dose of study medication. If urine pregnancy test cannot be confirmed as negative, a serum pregnancy test is required.
- c. Details for collection can be found in Section 7.1.3, Laboratory Procedures/Assessment.
- d. If the subject signs the Future Biomedical Research consent, any leftover samples that would be ordinarily discarded at the end of the main study will be retained for Future Biomedical Research.
- e. Tumor imaging (ie. CT scan, MRI, CT/PET, etc.) should be performed within 28 days of enrollment. Tumor imaging and response assessment(s) to be performed 12 weeks after first dose, than every 12 weeks until discontinuation or End of Treatment. Imaging assessments should be repeated every 12 weeks and follow calendar days and should not be adjusted for delays in Cycle starts or extensions of dosing frequencies. The same imaging technique should be used on a subject throughout the trial. Scans used for tumor measurements may be requested for central review.
- f. Laboratory tests at Screening are to be performed within 7 days prior to the first dose of study treatment.

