7.1.5.2 Treatment Period

Visit requirements are outlined in Section 6.0 - Trial Flow Chart. Specific procedure-related details are provided above in Section 7.1 - Trial Procedures.

After a screening phase of up to 28 days, eligible subject(s) will be assigned a dose levels by the sponsor. MK-1966 and SD- 101 treatment will be administered as outlined in Section 5.2 for 8 cycles (approximately 24 weeks) of study medication in Part A, B, C, or administrative reasons requiring cessation of treatment. After the end of treatment (EOT), each subject will be followed for 30 days. Serious adverse events (SAEs) will be collected for 30 days after EOT.

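### The compliance formulas in SAP section 8.8 do not match Table 5: a subject dosed exactly on schedule for all 8 cycles scores 200% for MK-1966 and 125% for SD-101

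*Combined protocol and SAP*

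**What the plan says.** Section 8.8 commits to a figure for every subject and each drug: "Percent compliance with drug administration will be calculated for each subject for MK-1966 and SD-101 separately". The ratio is doses taken over doses due, times 100. For MK-1966 the doses due "will be calculated as the minimum of the two numbers: 4 and (1 plus the number (integer) of 3-week intervals" between the first and last dose of that drug. For SD-101 they "will be calculated as 1 plus the number (integer) of 3-week intervals that fit between the date of the first dose" and the last dose, without a cap.

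Table 5 (section 5.2) sets the planned regimen, identical in Part A and in Parts B and C. MK-1966 is given on "Day 1 then Q3W for 7 additional doses", which is 8 doses. SD-101 is given on "Days 1, 8, 15, 22 then Q3W for 6 additional doses", which is 10 injections. Section 7.1.5.2 confirms treatment "for 8 cycles (approximately 24 weeks) of study medication in Part A, B, C", and footnote s of the Trial Flow Chart (section 6.0) puts the end of Cycle 8 at Day 168.

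**The concern.** An adherence percentage should equal 100% for a subject who takes every scheduled dose and fall below 100% for one who misses some. These formulas fail on both counts. The MK-1966 cap of 4 is half the planned number of doses, and nothing in the documents explains it. The SD-101 count treats the drug as given purely every 3 weeks and so omits two of the four injections due by Day 22.

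As a result, full adherence reads above 100%, and partial adherence can read exactly 100%. Truncating the output at 100% would not help, because subjects with missed doses would then look the same as subjects with none.

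**Working it through.** The documents state no expected compliance value, so there is no figure to reproduce. The check puts the Table 5 dosing days through the section 8.8 formulas.

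**Inputs**
- MK-1966 days (Table 5): 1, 22, 43, 64, 85, 106, 127, 148.
- SD-101 days (Table 5): 1, 8, 15, 22, 43, 64, 85, 106, 127, 148.
- MK-1966 doses due (8.8): min(4, 1 + floor((last day − first day)/21)).
- SD-101 doses due (8.8): 1 + floor((last day − first day)/21).

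**Completer on schedule.** Day 1 to Day 148 is 147 days, and 147/21 = 7.
- MK-1966: min(4, 1 + 7) = 4, so 8/4 = 200%.
- SD-101: 1 + 7 = 8, so 10/8 = 125%.

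**All scheduled doses taken up to a given day**

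| Last day dosed | MK-1966 taken / due by 8.8 | Score | SD-101 taken / due by 8.8 | Score |
|---|---|---|---|---|
| 1 | 1/1 | 100% | 1/1 | 100% |
| 8 | 1/1 | 100% | 2/1 | 200% |
| 15 | 1/1 | 100% | 3/1 | 300% |
| 22 | 2/2 | 100% | 4/2 | 200% |
| 43 | 3/3 | 100% | 5/3 | 167% |
| 64 | 4/4 | 100% | 6/4 | 150% |
| 85 | 5/4 | 125% | 7/5 | 140% |
| 106 | 6/4 | 150% | 8/6 | 133% |
| 127 | 7/4 | 175% | 9/7 | 129% |
| 148 | 8/4 | 200% | 10/8 | 125% |

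**Missed doses that do not show**
- SD-101 without Days 8 and 15, the other eight given: 8/(1 + 7) = 100%. Against Table 5: 8/10 = 80%.
- MK-1966 on Days 1, 43, 85 and 127 only: 126/21 = 6, min(4, 7) = 4, so 4/4 = 100%. Seven doses were due by Day 127: 4/7 = 57%.

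**Missed doses that do show.** MK-1966 on Days 1 and 43 only: 42/21 = 2, so 2/(1 + 2) = 67%, which is correct. Misses after a drug's last received dose never enter the denominator. That matters only if the drug had not been discontinued.

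**Early last dose.** From Cycle 3, section 5.2.5 allows this: "Trial treatment may be administered up to 3 days before or 5 days after the scheduled Day 1 of each cycle". With no earlier net delay, a last dose 1 to 3 days early loses a whole interval in the integer count.
- SD-101 tenth injection on Days 145–147: 1 + floor(144 to 146 / 21) = 7, so 10/7 = 143%.
- MK-1966 third dose on Days 40–42: 3/2 = 150%. Fourth dose on Days 61–63: 4/3 = 133%.
- MK-1966 eighth dose on Days 145–147 with the cap removed but the integer count kept: 8/7 = 114%. Lifting the cap alone is therefore not enough.

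**Delayed cycles.** The Flow Chart foresees them: imaging "should not be adjusted for delays in Cycle starts or extensions of dosing frequencies". Suppose all doses are given but later ones are deferred:
- 21 days (last on Day 169): SD-101 10/(1 + 168/21) = 10/9 = 111%.
- 42 days (Day 190): 10/(1 + 189/21) = 10/10 = 100%.
- 63 days (Day 211): 10/(1 + 210/21) = 10/11 = 91%.

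MK-1966 stays at 8/4 = 200% in each case.

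**The case against.** The strongest reply is that little depends on this number. Compliance is not an endpoint and no decision rule cites it. Site staff give and record the doses, and section 8.9 reports the doses actually received. A value of 200% would be noticed and could be corrected through the supplemental SAP provided for in section 8.0. Treatment lasts up to 8 cycles, so 200% applies only to completers, and the documents do not say how many subjects will pass Cycle 4. All of this is fair and limits the importance of the point. It does not make the formulas right. The SD-101 error already appears on Day 8, and a misleading 100% would not be noticed in the output.

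A second reply is that an omitted dose need not be non-adherence. Table 7 requires holds, section 5.2.5 permits interruptions, section 5.7.1 lets an injection be skipped with the Medical Monitor's agreement, and section 5.9 allows treatment to restart after discontinuation. The 80% and 57% comparators therefore mean share of scheduled doses received, not fault. This stands as a reason to state how such doses count. It does not defend section 8.8, which already counts omissions between first and last dose as due, apart from those lost to the cap or to the missing Day 8 and Day 15 terms.

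Third, section 8.5.2 bases the PK and target engagement population partly on compliance, including exposure. It does not cite the section 8.8 percentage, so no effect on those analyses is claimed.

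**Conclusion.** The concern holds. Followed exactly, section 8.8 gives an on-schedule completer 200% for MK-1966 and 125% for SD-101. MK-1966 is overstated from dose 5 (Day 85). SD-101 is overstated from the second injection, and 125% is the smallest excess once more than one injection has been given on schedule. Either drug can read 100% for a subject who missed doses.

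These figures assume dosing on the Table 5 days. Long deferrals shrink the SD-101 excess and eventually reverse it; they leave the completer's MK-1966 figure unchanged.

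The consequence is confined to a descriptive per-subject percentage. DLT evaluability (5.2.4, 8.5.1), the PK and target engagement summaries (8.6.3.2) and extent of exposure (8.9) are not defined through it. It should be corrected, but no primary conclusion depends on it.

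**What to change.** Reconcile section 8.8 with Table 5 by counting doses due by scheduled visit, not by elapsed 21-day intervals.

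- **MK-1966:** Day 1 of each cycle, maximum 8; remove the cap of 4.
- **SD-101:** Days 1, 8, 15 and 22, then Day 1 of each cycle from Cycle 3, maximum 10.
- **Both:** count doses due up to discontinuation of that drug or end of treatment. A subject taken off one agent, as section 5.2.3.1 can require in Parts B and C, is then not scored as non-compliant. For example, MK-1966 stopped after Cycle 4 while SD-101 continues gives 4/4 = 100%, not 4/8 = 50%.
- Add a sentence on how held, agreed-skipped and restarted doses are counted.

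Under this rule a completer scores 8/8 and 10/10, and omitting SD-101 on Days 8 and 15 shows as 8/10 = 80%. A dose given a few days early no longer changes the count. The cost is one derivation change in the SAP, with no new data. No change to dosing is implied.

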8.9 Extent of Exposure

A subject’s extent of exposure to MK-1966 is defined as the total number of doses of MK-1966 the subject received. A subject’s extent of exposure to SD-101 is defined as the total number of doses of SD-101 the subject received.

Extent of Exposure will be summarized for MK-1966 in combination with SD-101 dose levels with at least 3 subjects enrolled and listed for other dose levels.

9.0 LABELING, PACKAGING, STORAGE AND RETURN OF CLINICAL SUPPLIES

9.1 Investigational Product

The investigator shall take responsibility for and shall take all steps to maintain appropriate records and ensure appropriate supply, storage, handling, distribution and usage of

investigational product in accordance with the protocol and any applicable laws and regulations.

Clinical Supplies will be provided by the Sponsor as summarized in [Table 13](#).

Clinical supplies will be packaged to support enrollment and replacement subjects as required. When a replacement subject is required, the Sponsor or designee needs to be contacted prior to dosing the replacement supplies.

Table 13 Product Descriptions

Product Name & Potency	Dosage Form
MK-1966 50 mg/mL, 4 mL	Concentrate for solution for infusion
SD-101 16 mg/mL, .75 mL	Injection

Other supplies not indicated in [Table 13](#) may be provided centrally by the Sponsor or locally by the trial site, subsidiary or designee, depending on local country operational or regulatory requirements.

The trial site will be responsible for recording the lot number, manufacturer and expiry date of any locally purchased product.

